6.3 Treatment with Study Drugs

Treatment consisting of **LEN** and **MOR00208** combination will be administered up to twelve 28-day cycles at specified dose levels as scheduled until disease progression, unacceptable toxicity, or discontinuation for any other reason, whichever comes first.

LEN can be given for up to 12 cycles in total. Treatment with LEN will have to be stopped after disease progression. On days when both study drugs are given together, LEN should be administered prior to MOR00208.

MOR00208 can be administered at the dose and schedule described in [Section 6.1](#) above, until disease progression, unacceptable toxicity, or discontinuation for any other reason, whichever comes first.

It is up to the investigator to decide according to the individual risk/benefit ratio if the patient should further continue on MOR00208 in case of disease progression, after discussion with the Sponsor's Medical Monitor or designee. For patients who will be administered MOR00208 despite progression of disease / relapse, an **Unscheduled Visit** including all protocol prescribed procedures for the **EOT Visit** (except the PK sample and the anti-MOR00208 antibody sample) need to be performed in order to capture the event (i.e. disease progression/relapse) for the antibody treatment to continue further ([Table 5](#)). In such cases an **EOT Visit** will take place after these patients have finally stopped receiving the antibody. And lastly, a **Safety Follow-Up** will take place **30-Days** after last administration of MOR00208.

For patients receiving antibody treatment despite disease recurrence/progression, before the administration of MOR00208, blood parameters (haematology, serum chemistry) should be evaluated in the local lab according to local guidelines/standards of local medical practice for the administration of monoclonal antibodies. A urine pregnancy test should be performed for women of childbearing potential. Vital signs should be measured according to local practice for the administration of monoclonal antibodies. For this patient population only the antineoplastic therapy after the end of study drug combination treatment and AEs need to be captured in eCRF. Other procedures described in the column "MOR00208 Additional Treatment" in [Table 5](#) will not apply for this patient population.

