Patients should not have received a CD20-targeted therapy, chemotherapy, radiotherapy, investigational anticancer therapy or other lymphomaspecific- therapy within 14 days prior to Cycle 1 day 1 of the study. In addition, no radiotherapy (including limited field radiotherapy) is permitted after the baseline PET/CT scan for initial disease assessment has been performed. Other than the study drugs, patients should not receive any other DLBCLspecific- therapy during the study treatment period. The patient should not receive any investigational agent other than MOR00208 and LEN during the treatment period of the study.

The use of concurrent antineoplastic therapies other than study drugs, including, but not limited to, chemotherapies, hormonal therapy, immunotherapy, biological response modifiers, mAbs with or without conjugation, radioisotopic therapies, stem cell transplant and targeted small molecules are not permitted during the entire treatment period (i.e., prior to disease progression during this study) of this study. After disease progression has been recorded, additional antineoplastic therapies are permitted at the discretion of the investigator and in accordance with the local guidelines and should be recorded in the eCRF.

Systemic Glucocorticosteroids

The use of systemic glucocorticosteroids is generally discouraged because their potential antilymphoma activity in patients with DLBCL may confound interpretation of antitumor effects mediated by study drug treatment (MOR00208 and LEN).

However systemic corticosteroids in doses up to 20 mg/day prednisone or equivalent (i.e. equipotent corticosteroid) are permitted, provided the dosing is stable (not increased within the last month), but only for the treatment of non-neoplastic comorbid indications (e.g. rheumatoid arthritis).

-Screening:

Patients may potentially receive systemic glucocorticosteroids in doses above 20 mg/day (prednisone or equivalent) to manage severe DLBCL manifestations (e.g., compressive disease, rapidly progressing symptomatic adenopathy) during Screening as per institutional standards. For these patients the glucocorticosteroids treatment needs to be tapered to a total daily dosage of 20 mg or less of prednisone or its equivalent prior to study drug(s) administration on Cycle 1, Day 1.

-Cycle 1 through EOT visit:

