22.1.1 Treatment-emergent adverse events

An **on-treatment adverse event (or Treatment-emergent Adverse Event – TEAE)** is defined as any adverse event reported in the following time interval (including the lower and upper limits): date of first administration of any study drug; date of last administration of any study drug + 30 days.

If the last date of study drug administration is missing, on-treatment assessments/events include any assessment/event recorded in the database and which occur after the start date of study treatment. Safety summary tables including summaries of on-treatment deaths will be based only on on-treatment assessments/events.

An adverse event present prior to study drug administration but increased in severity after treatment start, will also be included as TEAE.

Events with missing onset dates will be included as TEAE if the end date is not before the start date of treatment.

Adverse events occurring or worsening later than 30 days after the date of last study drug administration or the date of completion/discontinuation of the study are defined as TEAE if these are considered to be related to the study drug.

If the start date and time of an AE are partially or completely missing, the AE will be assumed to be a TEAE if it cannot be definitely shown that the AE did not occur or worsen during the treatment-emergent period (worst case approach). Missing dates and times will not be replaced.

Thus, the following approach will be taken:

- If the start time of an AE is missing but the start date is complete, an AE will only be excluded from TEAE if start day is before day of first treatment or start day is after end day of treatment-emergent period.
- If start time and day are missing but the start month is complete, an AE will only be excluded from TEAE if start month is before month of first treatment or start month is

-
- after end month of treatment-emergent period or if stop date/time is before start of first treatment.
- If start day and months are missing but the start year is complete, an AE will only be excluded from TEAE if start year is before year of first treatment or if start year is after end year of treatment-emergent period or if stop date/time is before start of first treatment.
 - If start date is completely missing, an AE will not be excluded from TEAE unless the stop date/time is before start of first treatment.

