16.5 Subgroup analyses

16.5.1 Patients who discontinued LEN treatment

Efficacy assessment

A Kaplan-Meier analysis on PFS and OS will be conducted as described in Sections 10.2 and 10.4 for those patients who discontinued LEN treatment at any point in time. That is, regardless whether the discontinuation is due to an adverse event, or as per protocol after Cycle 12. The analysis will start from the moment of LEN discontinuation (zero time elapsed). Both Tables and Kaplan-Meier curves will be produced based on the FAS.

Safety assessment

Incidence and frequency of adverse events will be displayed separately for the periods *before* LEN discontinuation, and *after* LEN discontinuation. All discontinuations of LEN treatment are considered, regardless of the reason for discontinuation (per protocol, or due to AE).

TEAEs are considered for the **pre**-LEN discontinuation period if they are observed in the following interval (including the lower and upper limits): date of first administration of study treatment to date of last administration of LEN + 7 days (or if they are suspected to be related to LEN).

TEAEs are considered for the **post**-LEN discontinuation period if they are observed in the following interval (including the lower and upper limits): date of last administration of LEN + 8 days to date of last administration of MOR00208 + 30 days (if they are not suspected to be related to LEN).

For both periods following will be summarized by SOC, PT, and NCI-CTCAE Grade for the SAF:

- All TEAEs
- TEAEs by ,Search Category' (see Section 16.3.1)
- SAEs
- AESIs
- G3 vs. G4 TEAEs

Moreover, a Table summarizing fatal TEAEs (i.e., Grade 5 SAEs) will be produced.

A barplot will be produced illustrating the TEAEs that happened with an incidence of $\geq 10\%$ of patients in the SAF. Each bar will represent a particular PT, and for each bar the fraction of patients with Grade 1, 2, 3, 4, 5 will be indicated by color-coding or shading.

Exposure as described in Section 8.9.2 will be calculated for both the **pre**-LEN discontinuation period (exposure to LEN or the combination LEN/MOR00208), and the **post**-LEN discontinuation period (exposure to MOR00208). The exposure to LEN or the combination for the **pre**-LEN discontinuation period is starting from the first date of LEN dosing. The exposure to MOR00208 only for the **post**-LEN discontinuation period is starting from the first administration of MOR00208 after the discontinuation of LEN.

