20.11.3 TEAEs per patient years of exposure to MOR00208

Summary across both treatment phases:

Based on the SAF, the absolute number of TEAEs (i.e., the actual number of events) by patient years of exposure will be summarized by SOC, PT and NCI-CTCAE Grade. For the summary, patient years of exposure will be defined as follows:

$[(\text{end date of the MOR00208}) - (\text{start date of MOR00208}) + 1] / 365.25$.

The TEAEs per patient years of exposure will be reported with three decimal places.

Summary by treatment phase:

Based on the SAF, the number of TEAEs (i.e., the actual number of events) by patient years of exposure to combination treatment vs. MOR00208 monotherapy treatment will be summarized by SOC, PT and NCI-CTCAE Grade. Summaries will be provided separately for the combination treatment (MOR00208 + LEN) and MOR00208 monotherapy phase.

- Exposure to the combination treatment is defined as follows:

$[(\text{Latest date when at least one of either study drug has been discontinued}) - (\text{earliest date when the patient is treated with both study drugs}) + 1] / 365.25$.

Due to the fact that patients may discontinue LEN before reaching Cycle 12 Day 21 (i.e., the time when LEN is discontinued as per protocol), combination treatment may stop before completing 12 Cycles of LEN.

- Exposure to MOR00208 monotherapy treatment is defined as follows:

$[(\text{Discontinuation date of MOR00208}) - (\text{earliest date of MOR00208 infusion after LEN has been permanently discontinued}) + 1] / 365.25$.

Due to the fact that patients may discontinue LEN before reaching Cycle 12 Day 21 (i.e., the time when LEN is discontinued as per protocol), MOR00208 monotherapy treatment may start before reaching Cycle 13 Day 1. The TEAEs per patient years of exposure will be reported with three decimal places.

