23. SAP ADDENDUM 8.0

23.1.1 TEAEs per patient years of exposure to MOR00208 and LEN

Summary across both treatment phases:

Based on the SAF, the absolute number of TEAEs (i.e., the actual number of events) by patient years of exposure will be summarized by SOC, PT and NCI-CTCAE Grade. For the summary, patient years of exposure will be defined as follows:

Exposure to the treatment phase is defined as per section 8.9.2 and all TEAEs are counted.

The TEAEs per patient years of exposure will be reported with two decimal places.

Summary by treatment phase:

Based on the SAF, the number of TEAEs (i.e., the actual number of events) by patient years of exposure to combination treatment vs. MOR00208 monotherapy treatment will be summarized by SOC, PT and NCI-CTCAE Grade. Summaries will be provided separately for the combination treatment (MOR00208 + LEN) and MOR00208 monotherapy phase.

- Exposure to the combination treatment is defined as per section 8.9.2:

However, for the counts of TEAE the period considered is the earliest date when the patient is treated with both study drugs till the latest date when LEN has been discontinued.

Because patients may discontinue LEN before reaching Cycle 12 Day 21 (i.e., the time when LEN is discontinued as per protocol), combination treatment may stop before completing 12 Cycles of LEN. The definition of TEAE still applies when AE occurs beyond the discontinuation of LEN for the next 30 day follow up period. For patients who do not continue to monotherapy, any TEAE beyond 30 day follow up and related to either of the drugs will be considered in the combined therapy only. For the others who continue on to monotherapy the TEAEs beyond 30-day period are included in the monotherapy phase.

-
- Exposure to MOR00208 monotherapy treatment is defined as per section 8.9.2:

However, for the counts of TEAE the period considered is 1 day after LEN has been permanently discontinued till the discontinuation date of MOR00208.

Because patients may discontinue LEN before reaching Cycle 12 Day 21 (i.e., the time when LEN is discontinued as per protocol) or they have not received any dose of LEN, MOR00208 monotherapy treatment may start before reaching end of Cycle 12. The definition of TEAE still applies when AE occurs beyond the discontinuation of MOR00208 for the next 30 day follow up period. Any TEAE which still occurs beyond the 30 day follow up period will only be included if the AE is related to MOR00208.

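### The MOR00208 monotherapy safety phase does not end or split when another antineoplastic drug is added after progression

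*SAP*

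**What the plan says.** Three places in the SAP separate safety on the combination from safety on MOR00208 without LEN.

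- **SAP 20.11.3** defines monotherapy exposure only. It runs from the "earliest date of MOR00208 infusion after LEN has been permanently discontinued" to the "Discontinuation date of MOR00208".
- **SAP 23.1.1 (Addendum 8.0)** takes exposure from 8.9.2 and gives the event window: "the period considered is 1 day after LEN has been permanently discontinued till the discontinuation date of MOR00208". A further 30 days follow, and after that only events related to MOR00208 count.
- **SAP 16.5.1** sets the post-LEN event period as "date of last administration of LEN + 8 days to date of last administration of MOR00208 + 30 days", leaving out events attributed to LEN. An alternative version starts at day 31. The matching exposure is described as MOR00208 only.

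The general TEAE window, in the treatment-emergent subsection of SAP 10.7.3 (numbered 22.1.1), is "date of first administration of any study drug; date of last administration of any study drug + 30 days".

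On treatment, Protocol 6.3 stops LEN at progression but leaves MOR00208 open: "It is up to the investigator to decide according to the individual risk/benefit ratio if the patient should further continue on MOR00208". Protocol 6.7 bars other antineoplastic drugs before progression and then allows them: "After disease progression has been recorded, additional antineoplastic therapies are permitted at the discretion of the investigator". Table 5 footnote 21 applies this to patients still receiving MOR00208 and has the added therapy recorded in the eCRF. Protocol 7.2.3 keeps AE recording open for the same patients.

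**The concern.** The phase split exists to show what MOR00208 does without LEN. For that, the period labelled monotherapy has to contain MOR00208 as the only antineoplastic agent. As defined, it starts when LEN ends, for whatever reason, and stops only with MOR00208. A patient who progresses, stops LEN, stays on MOR00208 and is given another antineoplastic drug remains inside it.

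That patient's events, tabulated by SOC, PT and grade regardless of relationship, and the matching person-time then sit in the monotherapy column. If the added drug causes cytopenias or infections, a reader would credit them to MOR00208 alone.

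**Working it through.** **Step 1. Follow one patient through the definitions.** There is no figure in the plan to reproduce, so the check is whether any rule removes the patient.

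| Event | Rule | Effect on the phase |
|---|---|---|
| Progression, LEN stopped | Protocol 6.3 | Monotherapy / post-LEN period opens |
| MOR00208 continued | Protocol 6.3, 7.2.3 | Period stays open |
| Other antineoplastic drug started | Protocol 6.7, Table 5 footnote 21 | No rule in 16.5.1, 20.11.3 or 23.1.1; period stays open |
| AE during this time | Protocol 7.2.3; SAP TEAE window | Counted in the phase |
| MOR00208 stopped | SAP 20.11.3, 23.1.1, 16.5.1 | Exposure ends; events run 30 days more in 16.5.1 and 23.1.1 |

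No step ends or splits the period. Because 6.7 bars added therapy before progression, the problem is confined to post-progression time.

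**Step 2. Size.** The documents give neither the number of such patients nor their time or event rates. Let T be the person-time in the phase, f the share of T on added therapy, r the true monotherapy rate and k·r the rate on added therapy. Then

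reported rate = [(1 − f)·T·r + f·T·k·r] / T = r·[1 + f(k − 1)].

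Reported rate divided by true rate, for assumed f and k:

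| f | k = 0.5 | k = 1 | k = 2 | k = 3 | k = 5 |
|---|---|---|---|---|---|
| 2% | 0.99 | 1.00 | 1.02 | 1.04 | 1.08 |
| 5% | 0.975 | 1.00 | 1.05 | 1.10 | 1.20 |
| 10% | 0.95 | 1.00 | 1.10 | 1.20 | 1.40 |

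Example with assumed inputs: 50 patient-years at 4.0 events per year plus 5 patient-years at 12 per year gives (200 + 60)/55 = 4.73 per year against a true 4.00, or 18% too high. The formula agrees: f = 5/55 = 0.091 and k = 3 give 1 + 0.091 × 2 = 1.18.

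**Step 3. What the formula leaves out.** It assumes that events and person-time cover the same interval. In 23.1.1 events run 30 days past the end of MOR00208, while exposure under 8.9.2 ends one dosing interval less a day after the last infusion (13 days from Cycle 4 onwards). Events under a next therapy started in that tail can therefore add to the numerator with no full matching person-time.

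**The case against.** The strongest reply is that this is a small, visible and partly deliberate feature of descriptive tables. The patients are still receiving MOR00208, so their events belong to MOR00208 exposure. The SAP also gives a reader some means to see the problem. Section 8 lists and summarises patients treated despite progression. Section 8.7.6 counts those given non-study cancer treatment before study treatment ended, by drug class, with listings. The AE listings give onset and relationship. Section 23.1.1 openly accepts overestimated phase rates in order not to understate them.

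Much of this is fair. The number of patients may be very small, and an all-inclusive table is a legitimate summary. But the counts and listings do not alter the phase rates, and the drug-related TEAE tables are not split by phase. The overestimation admitted in 23.1.1 is put down to the 30-day overlap between phases, not to added therapy. Section 16.5.1 removes events attributed to LEN but has no rule for any other drug.

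A reader might go further than the documents allow in three ways.

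- **PFS censoring.** Table 13 might be read as already ending study-only follow-up when new therapy starts, which would make the safety rule inconsistent with the efficacy rule. It does not. That row covers non-study treatment given before progression and censors at the last adequate assessment. The patients at issue here have already progressed.
- **Other safety tables.** The time-to-first-event table in 16.3.2 and the onset and duration tables in 20.13 might seem to be affected in the same way. They are not split by phase and make no monotherapy claim. Nor do the overall TEAE tables in 10.7.3.
- **Direction of the bias.** A reader might take it that the monotherapy rate must be too high. Person-time on added therapy also enters the denominator, so the rate rises only if k exceeds 1, and falls if k is below 1.

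**Conclusion.** The concern holds as a mismatch between a label and its definition. Under 16.5.1, 20.11.3 and 23.1.1 as written, any time on MOR00208 plus another antineoplastic drug, and the events in it, is reported as MOR00208 without other therapy. That follows from the text whatever the number of patients.

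The size cannot be found from the documents. With f of 2 to 10% and k of 2 to 5, all assumed, the reported rate is 1.02 to 1.40 times the true one. If no patient receives added therapy during MOR00208, there is no effect. At k = 1 the rate is right, but the events by SOC and PT still mix two kinds of treatment. The primary endpoint is not touched. The change is worth making because these tables are the plan's main evidence on MOR00208 without LEN and the correction is cheap.

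**What to change.** In the phase-split tables of SAP 16.5.1 (both window definitions), 20.11.3 and 23.1.1:

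1. End both the events and the person-time of the monotherapy or post-LEN phase on the day before the first non-study antineoplastic therapy, if that comes before the present end. Apply this to the 30-day tail as well. A patient whose added therapy starts before the first post-LEN infusion contributes nothing to this column.
2. Show later events and person-time in a separate column, MOR00208 with other antineoplastic therapy, with the number of patients in it.
3. Keep the present all-inclusive version as a sensitivity table.

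Leave the overall TEAE tables in 10.7.3 as they are. No treatment rule changes.

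The cost is SAP wording and one date variable. The start date is already used in SAP 8.7.6, which even has a rule for therapy begun before the last study dose. The downside is slightly less exposure in the monotherapy column.

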20.12 TEAEs leading to study drug modifications

Based on the SAF, TEAEs leading to any Study Drug Modification of MOR00208 or LEN regardless of any study drug relationship by Primary SOC, PT and NCI-CTCAE Grade will be tabulated. TEAEs leading to the following modifications will be reported separately by modification category:

- Any modification (interruption or dose reduction)
- Interruptions
- Dose reductions (only applicable for LEN)

The TEAEs leading to the modifications mentioned above will be reported separately for:

- MOR00208
- LEN
- Any study drug

A Listing will be provided displaying TEAEs leading to study drug modifications (SAF).

20.13 Time to onset of individual TEAEs, duration of individual TEAEs, and cumulative duration of TEAEs per cumulative exposure to tafasitamab

For the categories listed below in this section, the following will be summarized based on the SAF:

- Time to TEAE onset [in days]
- TEAE duration [in days]
- Cumulative duration of TEAEs per cumulative exposure to MOR00208 [in months]
 - The cumulative duration of TEAEs will be reported in months
 - The cumulative exposure to MOR00208 will be calculated in years:
[(end date of the MOR00208) – (start date of MOR00208) + 1] / 365.25.

The summaries will be provided for the following categories:

- PT Neutropenia (all Grades)
- PT Neutropenia (\geq Grade 3)
- PT Thrombocytopenia (all Grades)
- PT Thrombocytopenia (\geq Grade 3)

STATISTICAL ANALYSIS PLAN

MorphoSys AG
MOR208C203

-
- SOC Infections and infestations (all Grades)
 - SOC Infections and infestations (\geq Grade 3)
 - SMQ "Infective pneumonia" (all Grades)
 - SMQ "Infective pneumonia" (\geq Grade 3)
 - CMQ "Urinary tract infection" (all Grades)
 - CMQ "Urinary tract infection" (\geq Grade 3)
 - CMQ "Sepsis" (all Grades)
 - CMQ "Sepsis" (\geq Grade 3)
 - CMQ "Opportunistic infections" (all Grades)
 - CMQ "Opportunistic infections" (\geq Grade 3)
 - PT Fatigue + PT Asthenia (all Grades)
 - All PTs including the verbatim Diarrhoea (all Grades)
 - PT Nausea + PT Vomiting (all Grades)
 - PT Febrile neutropenia (all Grades)
 - SMQ Thromboembolic event (all Grades)
 - SMQ Thromboembolic event (\geq Grade 3)

